#### **Exclusion criteria**

- Infant has any severe allergies (particularly corn or maize products, as probiotics and placebo powder contains maltodextrin)
- Infant has a disease that lowers their immunity (ie. leukaemia, cancer, HIV/AIDS)
- Infant is having treatment that lowers immunity (ie. steroids, immunotherapy, chemotherapy)
- Infant's mother is receiving highly immunosuppressive therapy (ie. biological disease modifying anti-rheumatic drugs (bDMARDs))
- Infant has had an immunoglobulin injection, received any blood products or blood transfusion)
- Infant has had a past history of Guillain-Barre syndrome
- Infant has a chronic illness
- Infant has a bleeding disorder
- Infant is ATSI (Aboriginal Torres Strait Islander)
- Infant does not have functional spleen
- Infant lives with someone who is immunocompromised (ie. leukaemia, cancer, HIV/AIDS, chemotherapy)

If any of the factors listed in the exclusion criteria (e.g. bleeding disorders, allergies to maize) are unknown at the beginning of the study and are discovered during the study, the infant has to withdraw from the study, and standard medical care and follow-up will be provided.

### **Intervention/ Comparison**

Sample size: n=50

Active group: n=25

Placebo group: n=25

**Active group:** 1000 IU Vitamin D & 2.3g Probiotics daily for 2 months

**a) Vit D3 Metagenics 1000 IU with 0.25ml dropper**

Metagenics Vitamin D3 90 mL oral liquid (360 days)

Storage: Store below 30°C. After opening store at 2°C to 8°C. (Refrigerate. Do not freeze.)

**b) Probiotics High Strength Inner Health for Kids (Metagenics)**

Each 2.3 g dose (1 level metric teaspoon) contains a blend of probiotic strains:

6 billion *Lactobacillus rhamnosus* (GG) organisms (LGG®)

3.75 billion *Lactobacillus acidophilus* (NCFM) organisms

3.75 billion *Bifidobacterium lactis* (Bi-07) organisms

[figure not shown]
**Placebo group:**

a) Placebo liquid contains medium-chain-length triglycerides (Metagenics R0121)

b) Placebo powder contains maize maltodextrin (Metagenics R0232)

**TIME LINE**

**Appointments with doctor:**

**Outcome measures**

| Primary (1), Secondary (2) | Outcome measures         | Tests        | Equipment                         | Lab/ location | Time points              |
|----------------------------|--------------------------|--------------|-----------------------------------|---------------|--------------------------|
| 1                          | Tympanic ear temperature | Temp         | Thermometer                       | NIIM, home    | Daily incl 0, 4, 8 weeks |
| 1                          | Weight, Growth           | scales       | Growth chart, weight chart        | NIIM          | 0,4,8 weeks              |
| 2                          | Sleep / cry              | Q/ diary     | Daily diary for infant collection | NIIM, home    | Daily                    |
| 2                          | Other symptoms           | Q            | Colds, mouth ulcers, rashes       | NIIM, home    | 0,4,8 weeks              |
| 2                          | Mood/ Stress             | Bond Lader Q | Main carer                        | NIIM          | 0,4,8 weeks              |
| 2                          | Sleep                    | Q            | Main carer                        | home          | Daily                    |

## **Assessments:**

Baseline data collection:

- Infant's mother's Vit D supplementation & plasma levels (if known) – during pregnancy and current
- Birth week of gestation, prematurity
- Vaginal, or caesarean birth
- Vit K given to infant at birth?
- Any genetic screening or other test results
- Infant's medication, e.g. PPI for reflux

### **Growth: Weight and size**

For size and weight measurements, standard scales will be use available at the clinic at all appointments.

### **Other symptoms Questionnaire**

Incl. Common Cold Symptoms, mouth ulcers, rashes, other

### **Tympanic ear temperature**

Daily 7pm measurements using the Infrared Thermometer ET100B, available from Medshop Australia.

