## The Vaccination Infant Supplementation (VISS) Study

**Randomised placebo-controlled trial investigating the effect of 8 weeks supplementation with probiotics and vitamin D around routine childhood immunisation on infant's ear temperature, growth, and sleeping pattern in 4-24 month-old infants.**

Infant vaccination numbers in the city of Stonnington and Bundoora have declined over that past decade due to concern over the effect of vaccination. There has been increasing concern that vaccination may adversely affect a child's immune system. However, given the nature of vaccine preventable diseases it is understood that the advantages of disease prevention and vaccination in the community are a priority.

Recent evidence shows that Vitamin D and probiotic supplementation has a beneficial effect on a child's immune system.

This project aims to examine the effect of Vitamin D and probiotics on a child's immune function before and after vaccination in a placebo and treatment group. This project will assess temperature daily for 2 months, pre and post immunisation in a supplemented (Vitamin D and probiotic) and placebo group.

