## **STUDY DESIGN**

Randomised parallel double-blind placebo-controlled trial of 2 months duration investigating the effect of supplementation with vitamin D and probiotics on behavioural and physiological response in infants during routine childhood immunisation.

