#### **Visits & Assessments**

##### **Visit 1 – week 0 - baseline**

Enrolment, informed consent by GP and chief investigator TN.

Baseline data collection:

- Infant's mother's Vit D supplementation & plasma levels (if known) – during pregnancy and current
- Birth week of gestation, prematurity
- Vaginal, or caesarean birth
- Vit K given to infant at birth?
- Any genetic screening or other test results
- Infant's medication, e.g. PPI for reflux

Assessments: weight, growth, temperature, other symptoms, Carer: Mood Q

Supply of supplements for 4 weeks – and discussion of administration

Supply of diaries: Daily 7pm temperature, infant sleep/cry = infant home diary; Carer sleep diary = Length and Quality of sleep recorded daily)

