### **Visit 2 – week 4 – vaccination**

The infant will only be eligible to be vaccinated if its temperature had been less than 38 degrees Celsius in the 4 weeks prior vaccination and since enrolment (at week 0).

Eligibility will be assessed by phone call 1-2 days before the scheduled appointment by NIIM receptionists.

If the infant had run a temperature > 38C in the last 4 weeks, the appointment will be postponed until 4 weeks after the fever.

If eligibility criteria are met, the original appointment will be confirmed.

1) **Assessments:** Weight, growth, temperature, other symptoms, collection of infant home diary and carer sleep diary; Carer: Mood Q; Tolerability & compliance Q

2) **Vaccination:** first immunisation of the Australian standard paediatric immunisation schedule:

a) **Infanrix hexa:** combined Diphtheria-Tetanus-acellular Pertussis (DTPa), hepatitis B, poliovirus and haemophilus influenzae type B vaccine

b) **Prevenar 13:** Pneumococcal polysaccharide conjugate vaccine, 13-valent adsorbed

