***Infanrix hexa and Prevenar 13 Information sheets will be provided by TN to the participating carers.***

➤ Immunisation to be given by same medical doctor and investigator TN for all participants.

3) Supply of supplements for 4 weeks – and discussion of administration

Supply of diary: Daily 7pm temperature, infant sleep/cry

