### **Analysis**

Analyses will be performed using SPSS (PASW version 18). Statistical significance will be set at  $p < 0.05$ . Between-group differences will be analysed by ANOVA comparing data after vaccination at 4 weeks (mean of daily data 4-8 weeks incl temperature, sleep/cry, carer sleep; or infant weight/growth data or carer mood data at 8 weeks) to data before vaccination (mean of daily data 0-4 weeks; or at 0 and 4 weeks).

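### Home temperature, a primary outcome, is read once every 24 hours at 7pm even just after vaccination, so a fever shorter than a day can pass unrecorded in either arm

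*Protocol*

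**What the plan says.** The Outcome measures table codes tympanic temperature as primary, with time points given as "Daily incl 0, 4, 8 weeks". The section on tympanic ear temperature sets the clock time: "Daily 7pm measurements using the Infrared Thermometer ET100B, available from Medshop Australia".

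The diary issued at Visit 1 carries "Daily 7pm temperature, infant sleep/cry = infant home diary". The supply list at Visit 2, the vaccination visit, repeats it: "Supply of diary: Daily 7pm temperature, infant sleep/cry". Nothing adds home readings, a daily maximum or fever-triggered readings after the injections.

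The clinic temperature at Visit 2 belongs to the assessments, which are listed ahead of the vaccination step, so as written it does not cover the response. The other-symptoms questionnaire is given at weeks 0, 4 and 8 and does not list fever.

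The Study Design section states the interest as "behavioural and physiological response in infants during routine childhood immunisation". The Analysis section summarises temperature after vaccination as the "mean of daily data 4-8 weeks incl temperature, sleep/cry, carer sleep", set against the mean of weeks 0-4.

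**The concern.** The sampling rate is the same on an ordinary day in week 2 as on the night after the injections. After a daytime vaccination the first home reading falls at 7pm that day and the next one 24 hours later. The first night and the following day, where a temperature response to a vaccine could well lie, have no reading.

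This is a matter of data capture and cannot be left to a statistical analysis plan. Whatever summary is chosen later (mean, peak, or any value above a threshold), a rise that began and ended between two readings is not in the data. At stake is whether the pilot can describe the post-vaccination temperature response at all, and how high the recorded peaks are.

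**Working it through.** The protocol gives no figure for fever capture, so there is none to reproduce.

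**Inputs from the protocol.** One home reading per 24 h at 7pm (19:00), before and after vaccination; about 28 readings in each 4-week period.

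**Assumptions (not in the documents).** Vaccination time uniform over 09:00-17:00; onset lag uniform over 2-8, 4-12, 6-24 or 0-48 h after the injection; fever duration D of 6 or 12 h. A fever counts as captured if at least one reading falls within it.

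**Simple case.** If onset is uniform over the day, P(captured) = D/24 for D up to 24 h: 6/24 = 25%, 12/24 = 50%, 18/24 = 75%. With readings at 7, 13 and 19 h the gaps are 6, 6 and 12 h. A 6 h fever is then missed only if it starts between 19:00 and 01:00, so capture is 18/24 = 75%. A 12 h fever always meets a reading.

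**Onset timed from the injection.** Simulated capture, once daily against three times daily:

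| Onset after injection | 6 h fever, 7pm only | 6 h fever, 7am/1pm/7pm | 12 h fever, 7pm only | 12 h fever, 7am/1pm/7pm |
|---|---|---|---|---|
| 2-8 h | 58% | 63% | 63% | 100% |
| 4-12 h | 28% | 41% | 28% | 100% |
| 6-24 h | 11% | 72% | 39% | 100% |
| 0-48 h | 25% | 75% | 50% | 100% |

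**One row by hand (6-24 h, D = 6).** Onset time S = vaccination time + lag runs from 15:00 to 41 h (17:00 the next day), over a total area of 8 x 18 = 144.

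- *7pm only.* Capture needs S at or before 19, or at or after 37. Each is a corner triangle of area 4 x 4 / 2 = 8, so capture = 16/144 = 11%.
- *Three readings.* The fever is missed only if S lies between 19 and 25. That area is (8² - 4²)/2 + 8 x 2 = 24 + 16 = 40, so capture = 1 - 40/144 = 72%.

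**Effect on the planned mean.** A rise of 1-2 C seen in a single reading moves a 28-reading mean by 1/28 to 2/28, that is 0.04 to 0.07 C. Whether such a fever is caught or missed therefore barely alters the planned temperature summary.

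**The case against.** The strongest reply is that the protocol's temperature outcome is a 4-week mean of daily readings, with no fever rate or peak defined. The 38 C threshold is used for eligibility and for rescheduling Visit 2: "If the infant had run a temperature > 38C in the last 4 weeks, the appointment will be postponed until 4 weeks after the fever". A fixed clock time also standardises time of day, which is sensible for a before/after comparison of means from carer-collected data in a 50-infant pilot. This stands. It means the 7pm series should be kept, and that the loss falls on the description of the acute response and hardly at all on the planned mean. It does not close the gap, since the stated interest is the response around immunisation.

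A reader might go further and infer three things that the documents do not support.

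- *That a known difference in fever rates would be cut to a fraction.* No fever rate is defined and no expected rate is given, so any such figure rests on a supplied endpoint and supplied rates.
- *That the pilot's variance estimates would be too low.* The sample size section says the pilot is to provide baseline values and variance for a larger study; it does not mention event rates. For a mean of daily readings, sparser sampling normally makes each infant's value noisier, not less variable.
- *That the trial could show a spurious effect.* The schedule is the same in both arms. If the supplement shortened fevers, capture would differ by arm, but that would reflect a real effect.

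The size also depends on onset. For a 6 h fever, three readings gain only about 4 points if onset is 2-8 h after the injection, and about 61 points if it is 6-24 h.

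**Conclusion.** The point holds as a limitation of data capture that can be put right before the trial runs. One 7pm reading a day leaves a 24-hour gap straight after vaccination. Under the assumptions shown, it captures about 11-58% of 6 h fevers and 28-63% of 12 h fevers, against about 41-75% and 100% with three readings a day. Fever duration, onset and clinic hours are all assumed; for fevers approaching 24 h the problem fades (75% captured at 18 h with uniform onset).

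The consequence is lost sensitivity and an understated post-vaccination peak, on the same schedule in both arms. It is not a contradiction in the protocol, and it does not invalidate the planned comparison of 4-week means.

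**What to change.** Keep the 7pm reading for the 8-week series and the planned mean as they are. On vaccination day, from the time of injection, and on the next 3 days, add diary lines for 7am and 1pm, and record the clock time of vaccination. Compare the post-vaccination peak and the occurrence of any reading above 38 C between the randomised arms, as an added summary of the temperature outcome.

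Do not add readings before Visit 2. A between-arm comparison of post-vaccination values does not need them, and more readings in that period would raise the chance of seeing a value that triggers the postponement rule.

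Cost: at most 2 x 4 = 8 extra readings per infant (fewer in practice, because a 7am reading on vaccination day precedes a daytime injection), on the thermometer the family already has, plus one changed diary page. Some added readings may be missed. The 7pm-7am gap also remains, so a short fever confined to the night would still go unrecorded.

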### **Sleep/Cry questionnaire for infants**

Daily diary booklet assessing sleep and cry pattern of the infant will be provided to participants.

### **Sleep/ Mood of carer**

The **Bond Lader Mood Q** will be administered to the main carer at NIIM at each visit at 0, 4 and 8 weeks.

In addition, a **sleep diary** will be provided to the main carer, to record a summary of the daily sleep pattern including length and quality of sleep.

These Sleep & Mood Data of the main carer are collated as an indirect measure of the child's health, as the infant can't express in words about their feelings.

## **STUDY PLAN**

### **PARTICIPANT RECRUITMENT**

Patients will be recruited through the NIIM clinic newsletter, NIIM website, facebook, flyers, and advertisements in Melbourne (maternal outreach Booroondara and Stonnington).

#### **Enrolment & randomisation**

The doctor and chief investigator TN will meet patients at the NIIM clinic to confirm eligibility and to collect the infant's care givers informed consent. Two groups will be recruited into this pilot study, group 1: vaccination-naïve (not yet immunised) infants 4-24 months into the study, and group 2: vaccinated infants 4-24 months.

Eligible infants will be enrolled and randomised. A computer-generated permuted block randomisation schedule prepared by a researcher not involved in patient recruitment and data collection will be used to allocate patients to the active or placebo groups.

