### **Participants**

#### **Inclusion criteria**

- Group 1 (preferred): Infants who have not yet been immunised (age range: 4-24 months).
- Group 2: Infants who have been immunised (age range: 4-24 months).
- Parents have agreed to have their child immunised.
- Normal infant growth as per WHO growth charts:  
<http://www.education.vic.gov.au/Documents/childhood/parents/mch/mchgrowthboy24mths.pdf>
- <http://www.education.vic.gov.au/Documents/childhood/parents/mch/mchgrowthgirl24mths.pdf>
- No tympanic temperature > 38 degrees Celsius in the preceding 4 weeks prior to immunisation
- Infants currently breastfed (e.g. exclusively or breast and formula fed)
- Infants currently not taking supplements (Vitamin D and/or probiotics)
- Infants who will remain in the same routine with primary carers for the 2 month study period
- Willing to contribute 50% (\$30) of the cost price for ear thermometer

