### **Sample size & Justification**

A sample size of **50 participants:** Active group: Vit D + probiotic (n=25); Placebo group (n=25) suggested for this pilot study to obtain baseline values and variance for a larger study.

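### Two recruitment groups are defined by vaccination history, but no stratification by group is stated and the ANOVA has no group or age term, which costs balance and precision that are cheap to keep

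*Protocol*

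**What the plan says.** Protocol, Inclusion criteria, lists two classes of eligible infant. Group 1, marked as preferred, has not yet been immunised. The other is "Group 2: Infants who have been immunised (age range: 4-24 months"). Protocol, Enrolment & randomisation, repeats the division: "Two groups will be recruited into this pilot study". Neither section gives a quota or an expected mix.

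The same section describes allocation to active or placebo: "A computer-generated permuted block randomisation schedule prepared by a researcher not involved in patient recruitment and data collection will be used". It states no stratification factor, number of lists or block size.

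Protocol, Intervention/ Comparison, fixes only arm totals: "Sample size: n=50", "Active group: n=25", "Placebo group: n=25". Protocol, Sample size & Justification, gives the purpose of that number: "suggested for this pilot study to obtain baseline values and variance for a larger study".

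Protocol, Analysis, says "Between-group differences will be analysed by ANOVA", sets data after vaccination against data before it, and uses a 0.05 significance level. It mentions neither vaccination group nor age. The two groups are not used again after the enrolment section.

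**The concern.** The protocol itself treats vaccination history as important enough to define two groups and prefer one of them. Both groups span 4 to 24 months. The primary outcomes are ear temperature around a vaccination and weight/growth over eight weeks. It is plausible that the reaction to a vaccine depends on earlier doses, and that eight-week growth depends on age within this range. Comparing each infant with its own earlier data removes stable differences in level. It does not remove differences in change.

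Permuted blocks hold the arm totals near 25 and 25 but do not balance vaccination history within them. Two things are at stake. In the one trial that is run, the arms may differ by chance in a factor known at enrolment, and the stated model does not allow for it. In addition, spread between the groups goes into the error term. That lowers power and makes the variance carried to the larger study depend on whatever mix of infants happened to enrol.

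**Working it through.** **Inputs from the protocol.** N = 50, with 25 active and 25 placebo (25 + 25 = 50, which agrees). The significance level is 0.05, taken as two-sided. No effect size, SD or power is stated, so there is no power figure to reproduce.

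**Assumptions, not in the documents.** The number m of infants in one vaccination group is 10, 15, 20 or 25. The group difference in pre/post change, δ, is 0.5 or 1.0 within-group SD. The block size is 4. The age effect is not quantified.

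**1. Chance imbalance without stratification.** Let x be the number of the m infants who fall in the active arm, with x ~ Hypergeometric(50, m, 25). The difference in share between arms is |x − (m − x)|/25 = |2x − m|/25.

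| m | P(difference ≥ 20 points) | SD of difference |
|---|---|---|
| 10 | 0.074 | 11 points |
| 15 | 0.217 | 13 points |
| 20 | 0.148 | 14 points |
| 25 | 0.258 | 14 points |

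The probabilities do not rise steadily because 2x − m must be even when m is even. The smallest attainable difference of at least 20 points is then 6/25 = 24 points, against 5/25 = 20 points when m is odd. In simulation with blocks of 4 the frequencies were about 0.19 (m = 15) and 0.22 (m = 25). They are a little lower because an incomplete last block can leave the arms at 24 and 26.

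**2. Shift in the realised comparison.** A 20-point imbalance moves the unadjusted arm difference by 0.20 × δ:
- δ = 0.5: 0.10 SD
- δ = 1.0: 0.20 SD

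For scale, the standard error with no group spread is √(2/25) = 0.283 SD. The difference detectable with 80% power is (1.96 + 0.84) × 0.283 ≈ 0.79 SD.

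**3. Error variance.** With group share p = m/50, the unadjusted within-arm variance is 1 + p(1 − p)δ².
- m = 15: 1 + 0.21 × 0.25 = 1.05 (δ = 0.5); 1 + 0.21 × 1 = 1.21 (δ = 1.0)
- m = 25: 1 + 0.25 × 0.25 = 1.06 (δ = 0.5); 1 + 0.25 × 1 = 1.25 (δ = 1.0)

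The pooled variance is therefore about 5% to 25% above the within-group variance. The matching standard errors, 0.283 × √variance, run from 0.29 to 0.32 SD, as the simulation also shows.

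**4. Simulation** (20,000 runs under the null, 10,000 for power at 0.8 SD, m = 15 and 25).

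| Design and model | Type I error, overall | Type I error, given imbalance ≥ 20 points | Power |
|---|---|---|---|
| Unstratified, no group term, δ = 0.5 | about 0.05 | about 0.06 | about 0.77 |
| Unstratified, no group term, δ = 1.0 | about 0.05 | about 0.095 | 0.70 to 0.71 |
| Unstratified, group in model | about 0.05 | 0.04 to 0.05 | 0.78 to 0.79 |
| Stratified, group in model | about 0.05 | no such imbalance occurred | 0.79 to 0.80 |

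The mean estimate under the null was about zero in every row.

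**The case against.** A reader might infer that the design is biased. It is not: over all randomisations the unadjusted estimate centres on the truth and type I error is about 5%. The issue is chance imbalance in the realised trial, together with lost precision.

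A reader might also infer that the protocol runs one list across both groups. It does not say so. It is silent on strata, and the fair statement is that none is given.

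It is tempting to put the problem in degrees and say that imbalance would swamp any effect on temperature. The documents give no temperature effect or SD, so this cannot be supported. Suppose, purely as an assumption, that the groups differ by 0.3 °C. If that difference lasted all 28 days after vaccination, a 20-point imbalance would move the arm difference by 0.2 × 0.3 = 0.06 °C. If it were an acute reaction of two days, the 28-day mean would differ by 0.3 × 2/28 ≈ 0.02 °C and the shift would be about 0.004 °C. The answer rests entirely on the assumption.

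Three further objections carry weight. Covariates are often left to a statistical analysis plan, which may exist and is not at hand. Adjustment alone recovers most of the lost power. At 0.5 SD the loss is small, and nothing in the documents establishes 1.0 SD.

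These points lower the weight of the concern without removing it. The protocol does state a model, and that model omits both factors. A later analysis plan can add covariates but cannot rebalance infants already allocated. The pilot label does not dispose of the matter, because variance is what the pilot is meant to deliver and the protocol still sets a significance level for between-arm tests.

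**Conclusion.** The point stands as an inexpensive improvement to a small trial. It does not show that the planned comparison is invalid. The imbalance probabilities, 7% to 26%, rest on the stated 25 per arm and an assumed 10 to 25 infants in the smaller group. The consequences rest on assumed group differences in change. At 0.5 SD, power for a 0.8 SD effect falls from about 0.79 to about 0.77 and the pooled variance is about 5% to 6% too high as a within-group figure. At 1.0 SD, power falls to about 0.70 and the variance excess is 21% to 25%. If vaccination history and age have no bearing on pre/post change, nothing is lost beyond the chance to show it.

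A related conflict is in the text itself. Visit 2 – week 4 – vaccination prescribes the first immunisation of the schedule for all infants, yet group 2 consists of infants already immunised. Stratification does not resolve this.

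**What to change.** - **Enrolment & randomisation:** state that separate permuted-block lists are prepared for group 1 and group 2. Do not add an age stratum, since four strata would be too many for 50 infants.
- **Analysis:** include vaccination group as a factor and age as a covariate in the ANOVA. Report the residual within-group variance for planning the larger study. Give arm differences within each group descriptively only, without tests. If an analysis plan already contains these terms, align the protocol with it.
- **Visit 2 – week 4 – vaccination and Inclusion criteria:** the sponsor must reconcile the first immunisation prescribed for all infants with the inclusion of group 2.

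The cost is one extra list from the same researcher, at most one incomplete block per stratum (so arm totals may depart slightly from 25 and 25), and two model degrees of freedom. No additional infants, visits or measurements are needed, provided that age and vaccination history are recorded at enrolment, where eligibility already requires both.
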